## **Current Clinical Risk Scores**

Clinical risk scores do not bridge the critical gap to enable clinicians to individualize long-term treatment with DAPT. For example, Yeh and colleagues developed a predictive score, the DAPT score, which is a tool designed to simultaneously predict ischemic and bleeding risk (Yeh 2016). Registry data from Sweden (2006 to 2014) that followed 41,101 patients demonstrated that the score had a discrimination of 0.54 for cardiovascular and cerebrovascular events, and

0.49 for fatal or major bleeding (Ueda 2018). Thus, the DAPT score supports individualization of therapy, however, the predictive accuracy is not sufficient to effectively guide therapy.

[name] et.al. applied the DAPT score to patients enrolled in a single center pilot study ([name] 2020). Patients with DAPT score  $\geq 2$  had a predicted event rate of 7.6% and an observed event (MI, stroke, death) rate of 10.1%. High platelet FcγRIIa expression was evident in 55% of patients with DAPT  $\geq 2$ . The combination of DAPT  $\geq 2$  plus high platelet FcγRIIa expression was associated with an event rate of 15.4% whereas the combination of DAPT  $\geq 2$  plus low platelet FcγRIIa expression was associated with an event rate of 3.7% ( $p < 0.05$ ). The broad distribution of platelet FcγRIIa expression in patients with both high and low clinical risk scores and these study results suggest that platelet FcγRIIa expression can be used to discriminate higher and lower risk among patients categorized as high risk by clinical risk tools.

## **Platelet Function Testing**

Because increased platelet reactivity has consistently identified patients at greater risk of subsequent cardiovascular events (Breet 2010, Wisman 2014, Reny 2016), large clinical trials were designed to determine whether platelet function testing could effectively guide antiplatelet therapy. Two trials failed to demonstrate that currently available tests of platelet function can be used to guide treatment (Price 2011, Collet 2012). Specifically, the GRAVITAS trial (Gauging Responsiveness with A VerifyNow assay-Impact on Thrombosis And Safety) randomized patients with high platelet reactivity to standard compared with high dose clopidogrel (Price 2011). One proposed reason for the lack of efficacy in this study was that effective suppression of high platelet reactivity with high dose clopidogrel was not confirmed. The ARCTIC trial (Assessment by a Double Randomization of a Conventional Antiplatelet Strategy versus a Monitoring-guided Strategy for Drug-Eluting Stent Implantation and of Treatment Interruption versus Continuation One Year after Stenting) addressed this concern by employing a treatment strategy in which platelet function testing was used to confirm suppression of high platelet reactivity by augmenting treatment followed by confirmation that high platelet reactivity was suppressed (Collet 2012). The failure of ARCTIC suggests inadequate suppression of high platelet reactivity was not the mechanism responsible for failure. Thus, currently available platelet function tests are not capable of guiding individualized care. Intra-individual variability in platelet function over time is substantial and may be a major contributor to the failure (Frelinger 2013, Hochholzer 2014, Nührenberg 2015) as evidenced in the ELEVATE-TIMI 56 study where more than 40% of patients exhibited a greater than 20% change in platelet function over the course of 2 weeks (Hochholzer 2014).

## **Summary**

Cardiovascular disease is prevalent and recurrent cardiovascular events are a major cause of morbidity and mortality. An expanding armamentarium of therapeutic options that reduce cardiovascular risk underscores the promise of precision medicine that effectively tailors therapy to subsequent risk. Clinical risk tools and currently available tests of platelet function are not sufficient to effectively guide therapy.

## 2.2 STUDY HYPOTHESIS

Platelet expression of FcγRIIa is hypothesized to be a novel biomarker that, when quantified, can be used to identify patients at high and low risk of cardiovascular events. This hypothesis is based on the premise that currently available platelet function tests are analogous to a random glucose measurement and that platelet expression of FcγRIIa is analogous to an HbA1C, reflecting platelet reactivity over a longer interval of time. Because FcγRIIa amplifies platelet activation (Boylan 2008, Lova 2002) increased platelet expression of FcγRIIa will identify patients with consistently high platelet reactivity (Serrano 2007). Accordingly, high platelet expression of FcγRIIa leverages the clinical risk of increased platelet reactivity demonstrated by more than 100 studies and over 22,000 patients (Breet 2010, Wisman 2014, Reny 2016). Moreover, quantification of platelet FcγRIIa expression eliminates factors that cause variability with platelet function tests including the preparation of blood and the *in vitro* activation of platelets. The measurement of platelet expression of FcγRIIa does not require activation of platelets and platelet FcγRIIa does not exhibit the magnitude of intra-individual variability seen with platelet function tests.

Specifically, the study hypotheses are:

1. Platelet expression of FcγRIIa is associated with risk of MI, stroke, and death.
2. Incorporating platelet expression of FcγRIIa into existing risk scores improves identification of patients at high risk of MI, stroke, and death.
3. Platelet expression of FcγRIIa is not associated with risk of major bleeding.

## 2.3 EVIDENCE FOR USE OF FCγRIIA AS A TOOL

FcγRIIa, a member of the Fc family, is expressed on the surface of platelets and amplifies platelet activation (Boylan 2008, Lova 2002). Because FcγRIIa amplifies platelet activation (Boylan 2008, Lova 2002), greater expression increases platelet reactivity (Serrano 2007). In a single center pilot study, [name] et.al. found that high platelet expression of FcγRIIa ( $\geq 11,000/\text{platelet}$ ) was associated with a greater risk (odds ratio  $> 4$ ) of MI, stroke, and death ([name] 2018). Platelet expression of FcγRIIa does not require activation of platelets, is not affected by antiplatelet and anticoagulant agents, and does not exhibit the magnitude of intra-individual variability seen with platelet function tests (McMahon 2019). Further, clinical risk scores have demonstrated overlap between the risk of thrombotic/ischemic events and the risk of bleeding events (Hsieh 2017). Increased platelet expression of FcγRIIa was not associated with a greater risk of bleeding ([name] 2018) and may distinguish thrombotic risk from bleeding risk.

Evidence in support of platelet expression of FcγRIIa as an effective precision tool:

1. Platelet function tests demonstrate substantial intra-individual variability (Frelinger 2013, Hochholzer 2014, Nührenberg 2015), with more than 40% of patients exhibiting a  $> 20\%$  change in platelet function over the course of 2 weeks (Hochholzer 2014). Platelet FcγRIIa expression exhibits substantially less intra-individual variability (McMahon 2019). Platelet expression of FcγRIIa is determined by megakaryocyte production that was demonstrated to

be increased by interferon  $\gamma$  ([name] 2009). Thus, expression of Fc $\gamma$ RIIa should be consistent throughout the life of the platelet. Less intra-individual variability would be expected and has been observed (Figure 1). Consistent with these results, Calverley and colleagues found an average change in platelet Fc $\gamma$ RIIa expression of less than 10% in 248 patients with cardiovascular disease when repeat determinations were performed 6-52 weeks later (Calverley 2002).

2. Greater platelet expression of Fc $\gamma$ RIIa is associated with increased platelet reactivity because Fc $\gamma$ RIIa amplifies platelet activation (Boylan 2008, Lova 2002). Unlike currently available tests of platelet function that measure platelet reactivity in response to a select agonist or group of agonists, platelet expression of Fc $\gamma$ RIIa predicts increased platelet reactivity in response to a variety of agonists (Figure 2).
3. Because determination of platelet Fc $\gamma$ RIIa expression entails quantification of a surface marker, it is less sensitive to perturbations related to assay conditions (Table 1) (McMahon 2019). Neither anticoagulants nor a P2Y12 antagonist alter platelet expression of Fc $\gamma$ RIIa (McMahon 2019, Table 1).

[figure not shown]

Figure 1: Intra-individual variability in platelet expression of Fc $\gamma$ RIIa over the course of 1 month in healthy subjects (n=10). Because platelet function is known to exhibit diurnal variation, platelet expression of Fc $\gamma$ RIIa was assessed in the morning and afternoon as well as after 1 week and 1 month (McMahon 2019).

[figure not shown]

Figure 2: Activation of platelets identified by surface expression of P-selectin with the use of flow cytometry. Patients with end stage renal disease (n=33) were stratified into 2 groups on the basis of median expression of FcγRIIa. The percentage of platelets expressing P-selectin on their surface in the absence of agonist and in response to the collagen mimetic convulxin (1 ng/ml), platelet activating factor (PAF, 1 nM), adenosine diphosphate (ADP 0.2  $\mu$ M), or thrombin (1 nM) is shown. High platelet expression of FcγRIIa was associated with greater activation of platelets in response to each agonist (Serrano 2007).

Table 1: Intra-assay coefficient of variation (CV) for assay of platelet FcγRIIa expression

CV same anticoagulant	1.9% $\pm$ 0.5%
CV between anticoagulants	1.7% $\pm$ 0.5%
CV citrate anticoagulant vs citrate + cangrelor	0.7% $\pm$ 0.2%

Blood was taken from 3 subjects and anticoagulated with corn trypsin inhibitor (32  $\mu$ g/ml), trisodium citrate (3.2%), unfractionated heparin (1.2 U/ml), and bivalirudin (8  $\mu$ g/ml). Cangrelor (500 nM) was added to blood anticoagulated with citrate. Duplicate determination of platelet FcγRIIa expression in each condition (McMahon 2019).

In summary, platelet expression of FcγRIIa is a novel biomarker that appears to identify patients at high and low risk of subsequent cardiovascular events ([name] 2018). Because FcγRIIa amplifies the activation of platelets (Boylan 2008, Lova 2002) it is a marker of consistently increased platelet reactivity. Thus, platelet expression of FcγRIIa leverages results from multiple studies demonstrating that greater platelet reactivity is associated with a greater risk of cardiovascular events (Breet 2010, Wisman 2014, Reny 2016) with an assay not affected by antiplatelet or anticoagulant therapy that reproducibly identifies consistently increased platelet reactivity and may effectively discriminate residual cardiovascular risk and guide individualized treatment.

### FcγRIIa as a novel biomarker

FcγRIIa was identified as the low-affinity receptor for the fragment constant (Fc) portion of immunoglobulin (Ig) G (Karas 1982). Binding to FcγRIIa activates platelets. For example, platelets can coat an Ig-bound (opsonized) entity such as a bacterium via FcγRIIa and this

binding triggers platelet activation and release of secondary mediators that amplify the platelet response to a wide range of bacteria (Cox 2011, Arman 2014). In addition, platelet FcγRIIa is involved in heparin-induced thrombocytopenia and thrombosis, and the principal cellular target for anti-platelet factor 4/heparin antibodies is the platelet FcγRIIa receptor (Kelton 1988, Reilly 2001). FcγRIIa and glycoprotein VI are linked on human platelets, and ligands acting at either receptor activate dual proteolytic regulatory pathways (Gardiner 2008). FcγRIIa markedly enhances thrombus formation when platelets are perfused over a collagen-coated flow chamber under conditions of arterial and venous shear (Zhi 2013). More recently, an additional important function of platelet FcγRIIa has been defined. Phosphorylation of FcγRIIa amplifies the activation of platelets (Boylan 2008, Lova 2002). These observations led to assessing platelet reactivity in patients with end stage renal disease because these patients were known to exhibit increased platelet expression of FcγRIIa (El-Shahawy 2007). The reactivity of platelets with higher and lower platelet expression of FcγRIIa was compared and found that platelets with more FcγRIIa exhibited greater activation in response to sub-maximal concentrations of multiple agonists (Figure 2, Serrano 2007). Taken together, these results led to the hypothesis that high platelet expression of FcγRIIa is a novel biomarker of increased platelet reactivity.

Platelets from healthy young people carry 1,000-4,000 molecules of FcγRIIa (Karas 1982). Calverley and colleagues found that platelet expression of FcγRIIa was increased in patients with an acute coronary or cerebrovascular events as well as in patients with diabetes and individuals without cardiovascular events who had two or more cardiac risk factors (Calverley 2002). In addition, they found limited intra-individual variability when repeat determination was performed after 6-52 (average 20) weeks (Calverley 2002). These results suggest that, unlike measures of platelet function that exhibit marked intra-individual variability (Frelinger 2013, Hochholzer 2014, Nührenberg 2015), platelet expression of FcγRIIa is a consistent marker of increased platelet reactivity.

Flow cytometry is a powerful tool capable of assessing expression of FcγRIIa on the platelet surface. Platelets are identified by their size as well as a surface marker. Without a standardized measure of fluorescence intensity, results of analyses can be described only in relative terms of fluorescence intensity. The interpretation of fluorescence intensity measurements can be complicated by multiple factors including daily instrument variation, differences in hardware (laser power, filter sets), as well as the density of fluorochrome labeling of antibodies. A goal is to develop a clinically validated tool that can be used broadly in the care of patients, therefore external standards will be employed in the current study to enable the standardization of fluorescence intensity units (Kay 2006, Quadrini 2016). Accordingly, platelet expression of FcγRIIa will be quantified with the use of external standards to quantify the number of molecules on the platelet surface rather than relative platelet expression of FcγRIIa.

### **Prior study to evaluate FcγRIIa**

[name] et.al. completed a single center prospective trial designed to determine whether platelet expression of FcγRIIa would discriminate cardiovascular risk ([name] 2018). Patients (n=197) were enrolled shortly before discharge from a hospitalization for MI (both ST elevation and non-ST elevation were included). Although inclusion criteria allowed patients who

had been treated with PCI, coronary artery bypass grafting, or medically, all patients enrolled were treated with PCI. The primary endpoint, a composite of MI, stroke, death, and coronary revascularization, was lower in patients with platelet expression of FcγRIIa <11,000 (Figure 3). All patients were treated with ASA (81 mg) and treatment with clopidogrel (~64%) and ticagrelor (~36%) was balanced in patients with high and low platelet expression of FcγRIIa (Serrano 2007).

[figure not shown]

Figure 3: Summary of prospective single center study ([name] 2018)  
CVA=cerebrovascular accident, MI=myocardial infarction, Revasc=revascularization

Clinical characteristics of patients with high and low platelet expression of FcγRIIa were well balanced with the exception of older age, diabetes, and prior revascularization being more prominent in the high expression group. Cox multivariate analysis for the combination of MI, stroke, revascularization, and death demonstrated a hazard ratio of 3.0 ( $p=0.02$ ) for platelet expression of FcγRIIa  $>11,000$  when age, diabetes, and prior revascularization were included as covariates.

The incidence of revascularization was similar in patients with high and low platelet expression of FcγRIIa (low platelet FcγRIIa n=3, 3.2%; high platelet FcγRIIa n=4, 3.8%,  $p=0.815$ ). Patients with platelet expression of FcγRIIa  $\geq 11,000$  had a greater risk of MI, stroke, and death that became apparent after 6 months (Figure 4).

Cox regression analysis was performed and platelet expression of FcγRIIa was the sole covariate (hazard ratio 3.9,  $p=0.035$ ) associated with freedom from MI, stroke, and death.

[figure not shown]

Figure 4: Kaplan-Meier curves of the probability of freedom from MI, stroke, and death. The average duration of follow-up was 20 months (range 6-29 months).

MI=myocardial infarction

The predictive capacity of platelet expression of Fc $\gamma$ RIIa was evaluated. The sensitivity of high expression to identify patients with cardiovascular events was 0.82 (95% CI 0.57 - 0.92) and the specificity was 0.51 (95% CI 0.43 - 0.58). MI, stroke, and death were uncommon (8% of all patients) in patients who had had an MI. The negative predictive value of low platelet expression of Fc $\gamma$ RIIa was 0.97 (95% CI 0.89 - 0.98) and the positive predictive value of high platelet expression of Fc $\gamma$ RIIa was 0.14 (95% CI 0.10 - 0.46). While identification of patients at high risk has great value, the identification of patients at low risk is important to reassure clinicians that they can safely withhold therapy that is associated with a risk of complications. As is often the case for low prevalence events, the negative predictive value of platelet Fc $\gamma$ RIIa expression (97% [95% CI 89% - 98%]) offers potentially important guidance to clinicians.

A key objective of this study is to determine the optimal threshold of platelet Fc $\gamma$ RIIa expression that classifies patients as high and low risk that will, in turn, be incorporated into an individualized score designed to predict patient risk. Assessment of platelet Fc $\gamma$ RIIa expression as a continuous variable is expected to be more predictive than as a dichotomous variable. If assessment of platelet Fc $\gamma$ RIIa expression as a dichotomous variable is nearly as predictive as a continuous variable, then the simplicity associated with the definition of a threshold for high and low risk could be preferred.

Clinical criteria that identify patients at increased risk of thrombosis also identify an increased risk of bleeding (Lindholm 2019). A key feature predisposing to both thrombosis and bleeding is older age. Not surprisingly, patients identified as having an increased risk of ischemic events also exhibit a higher risk of bleeding events (Hsieh 2017, Lindholm 2019). In this pilot study, increased platelet expression of Fc $\gamma$ RIIa was not associated with a greater risk of bleeding

([name] 2018). Further, a meta-analysis of platelet function tests demonstrated that patients with high platelet reactivity were at lower risk of bleeding events compared with those who exhibit low platelet reactivity (Aradi 2015).

In summary, preliminary results demonstrate:

- Increased platelet FcγRIIa expression is associated with consistently increased platelet reactivity
- With appropriate calibration platelet expression of FcγRIIa can be quantified to enable comparison between centers and to assess changes over time
- Unlike platelet function tests, measurement of platelet expression of FcγRIIa is not substantially affected by conditions of the assay, antiplatelet therapy nor anticoagulant therapy
- Platelet expression of FcγRIIa  $\geq 11,000/\text{platelet}$  identifies patients with ~4-fold greater risk of MI, stroke, and death

### **Current Study**

Confirmation of results seen in the single center pilot study is necessary in a larger multicenter trial to validate the results of the pilot study and to determine whether platelet expression of FcγRIIa can be used to guide individualized precision therapy and improve outcomes. Results from the current study will determine the prognostic implications of platelet FcγRIIa expression as well as the optimal manner in which to use platelet FcγRIIa expression. The analysis plan will include assessment of platelet FcγRIIa expression as a continuous variable as well as a sensitivity analysis designed to determine whether FcγRIIa  $\geq 11,000/\text{platelet}$  is the optimal threshold for discrimination of risk. In addition, it will provide key preliminary evidence regarding prognostic implications of platelet FcγRIIa expression associated with anti-thrombotic regimens and support plans for a subsequent clinical trial designed to use platelet FcγRIIa expression as a precision tool.

To identify subjects at greater risk of events, subjects will be enrolled who have an increased risk of cardiovascular events based on results from the SWEDEHEART registry that analyzed 100,879 patients (Lindholm 2019). Hospitalized MI subjects with  $\geq 2$  of the following risk factors; age  $\geq 65$ , prior MI, diabetes mellitus, multivessel coronary artery disease (two or more vessels or left main with a stenosis  $\geq 50\%$  at coronary angiography) and chronic kidney disease (an estimated glomerular filtration rate below  $60 \text{ ml/min}/1.73 \text{ m}^2$ ) will be enrolled in the current study. In the SWEDEHEART registry, patients with  $\geq 2$  risk factors comprised 47% of patients and their risk of death, MI and stroke was 9.7/100 patient years. In the pilot study, 55% of subjects with increased risk based on clinical risk scores exhibited platelet expression of FcγRIIa  $\geq 11,000$  ([name] 2020). In the current study, enrollment of subjects receiving treatment with anticoagulant therapy (i.e., for treatment of atrial fibrillation, venous thromboembolism) will be limited to approximately 100 subjects. Subjects with non-cardiovascular conditions expected to limit survival to less than 2 years will be excluded in the current study.

Because high platelet expression of FcγRIIa increases platelet reactivity (Boylan 2008, Lova 2002), it is anticipated that despite an association between high platelet expression of FcγRIIa

and older age ([name] 2018), there will not be a significantly increased incidence of clinically significant bleeding, defined as BARC type 2-5, among patients with high platelet expression of FcγRIIa.

Lastly, to ensure consistent results, platelet expression of FcγRIIa will be quantified at a core laboratory. At clinical sites, citrate anticoagulated blood will be added to fixative tubes. These tubes will be shipped to the core laboratory for quantification of platelet FcγRIIa expression.

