#### 9.4.2 ANALYSIS OF THE PRIMARY OBJECTIVE

Cox proportional hazards models will be fit to compare the risk of the primary endpoint based on platelet expression of FcγRIIa as a continuous variable. Subjects will be followed until their earliest MI, stroke, or death. Patients who do not experience the composite endpoint will be censored at their last telephone follow-up. Time to the primary endpoint will be calculated as days from study enrollment. Models will be adjusted for potential confounders including sex and other subject demographics and medical history collected at baseline. In the pilot study, it was observed that older age, diabetes mellitus, and prior revascularization were associated with higher platelet FcγRIIa expression.

A set of sensitivity analyses will evaluate FcγRIIa as a binary endpoint, which each analysis using a different threshold for classifying FcγRIIa as high or low. In particular, these analyses will explore whether a binary or a continuous measure of FcγRIIa provides greater predictive value, and whether or not a threshold of  $\geq 11,000/\text{platelet}$  is optimal.

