A final set of exploratory analyses will be done to help determine the optimal threshold value of FcγRIIa for risk stratification. Define a threshold value, x, and define “low” FcγRIIa as a value less than or equal to x, and “high” FcγRIIa as a value greater than x. Next, calculate exposure-adjusted subject incidence rates for the primary endpoint, separately for the “low” and “high” subgroups, as the number of subjects with an event divided by the sum across subjects of the event/censoring times. Then, plot the exposure-adjusted incidence rates as a function of x for each subgroup, as well as the difference between subgroups. In addition, ROC curves will be produced showing the sensitivity and specificity of FcγRIIa to predict the presence or absence of a primary endpoint, as a function of the FcγRIIa threshold.

Flow cytometry considerations

[figure not shown]
Flow cytometry output, mean fluorescence intensity (MFI), can be influenced by multiple factors. External standards are used to translate MFI into molecules/platelet. In the original study, Bangs Laboratories Quantum MESF beads were used to translate MFI to antibody binding capacity ([name] et al). Because our antibody is labeled with 1 molecule of phycoerythrin (PE) per antibody, the antibody binding capacity equates to molecules per platelet.

Shortly before initiating the current study, Bangs Laboratory changed their calculation template. The company reported that over time their calculation template had experienced a shift (personal communication). This change led to a substantial change in the quantification. The change represents a ‘unit’ change rather than a complete revision of the translation of MFI into molecules/platelet.

Results using Bangs Laboratories Quantum MESF were compared with an independent external standard, BD Quantibrite. The two external standards (Quantum MESF and Quantibrite) yielded similar results. Based on this information, the revision of the formula by Bangs Laboratories was determined to be a more accurate assessment of molecules/platelet.

Results from the original study were analyzed with the use of the Quantibrite formula to relate results obtained using the previous Bangs Laboratories formula with the formula used with Quantibrite beads.

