5.7.2 Analysis of the Secondary Objective

First Secondary Objective: Negative predictive value, positive predictive value, sensitivity, and specificity will be calculated. Prediction will be performed using a Cox regression model with the following predictors: platelet expression of Fc γ RIIa, sex, age, and clinical risk factors associated with increased cardiovascular risk. Evaluation of the model's error rates will be based on a leave-one-out cross-validation approach. Additional models will evaluate the performance of the predictive model using a continuous measure of Fc γ RIIa with the performance of predictive models using various binary measures of Fc γ RIIa.

Second Secondary Objective: The adjusted Cox proportional hazards model described for the primary objective analysis will be used to compare the bleeding risk as a function of Fc γ RIIa expression. One

model will include FcγRIIa as a continuous variable, and another using the dichotomized version of FcγRIIa selected as the optimal version for risk stratification.

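### The SAP selects an FcγRIIa cut-off from the study's own data with no measure of its uncertainty and carries it into the bleeding model, although 1,750 is already specified as the high/low boundary

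*Protocol*

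**What the plan says.** The protocol background states "A key objective of this study is to determine the optimal threshold" (2.3, Prior study to evaluate FcγRIIa). The Current Study text plans a continuous analysis "as well as a sensitivity analysis designed to determine whether FcγRIIa" at or above the pilot value of 11,000/platelet "is the optimal threshold for discrimination of risk". Protocol 9.4.2 repeats that question among the sensitivity analyses and adds that "these analyses will explore whether a binary or a continuous measure of FcγRIIa provides greater predictive value".

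SAP 5.7.1 describes the method: "A final set of exploratory analyses will be done to help determine the optimal threshold value of FcγRIIa for risk stratification". For each cut-off x the analyst is to "plot the exposure-adjusted incidence rates as a function of x for each subgroup, as well as the difference between subgroups", and ROC curves are drawn over all cut-offs. It names no selection criterion, grid of values or interval for the chosen x, and no rule for when another value counts as better than the pilot value.

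Under Flow cytometry considerations, the same SAP section converts 11,000 to the current assay scale, rounds the result to 1,750, and says this value is to be tested and will define low versus high. SAP 5.7.2 nevertheless specifies, for the binary bleeding model, the version "selected as the optimal version for risk stratification". Nothing says which definition applies if the two differ.

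**The concern.** The best cut-off found in a data set performs at least as well in that data set as any cut-off fixed beforehand, whether or not it is better in truth. Without an interval, a reader cannot tell a real improvement on 1,750 from a chance one, and the selected cut-off's own performance is overstated.

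The result has uses. The protocol intends the threshold to enter an individualised risk score and to support a later trial, and SAP 5.7.2 lets it define the groups in the bleeding model. A value that moved by chance could be reported as correcting the pilot, then move again in the next cohort.

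**Working it through.** **1. The plan's own figure.** SAP 5.7.1 gives log(Quantibrite) = a·log(original) + b, with a = 0.9160084 and b = -1.0611595. Then exp(0.9160084 × ln 11,000 - 1.0611595) = 1,742.18, which matches the stated 1,742.183 and rounds to 1,750. The documents give no figure for how reliably the search recovers a cut-off.

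**2. Inputs.**
- 800 subjects and at least 80 events (Protocol 9.2).
- Twelve months of accrual plus 18 months gives mean follow-up of 18 + 12/2 = 24 months. At 10% a year (Protocol 4.1), expected events are 800 × (1 - exp(-0.10 × 2)) = 145. Eighty is therefore the floor, and about 145 is what the plan's own rate implies.
- Effect: 2-fold by design, about 4-fold in the pilot (Protocol 9.2).
- Share above the cut-off: the pilot's revascularization counts imply 3/0.032 ≈ 94 low and 4/0.038 ≈ 105 high, so about 53% high. The protocol gives 55% among pilot subjects at increased clinical risk.
- Assumptions not in the documents: lognormal FcγRIIa with SD of log 0.35 (0.25 and 0.50 also tried), the grids, and the criteria. The criteria are the Youden index (sensitivity + specificity - 1, from the ROC curve) and the difference in event rates per unit of follow-up (from the SAP plot).

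**3. The structural point.** For any criterion C, max over x of C(x) ≥ C(1,750). Equality holds only if 1,750 happens to be the maximum.

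**4. How often another value wins although 1,750 is truly best.** The hazard steps exactly at 1,750; 2,000 simulated trials per setting; 10-90% of subjects in each group.

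| HR | Events | Youden, all observed values | Youden, 50-unit grid | Rate difference, 50-unit grid | Youden, 250-unit grid |
|---|---|---|---|---|---|
| 2 | 80 | 98% | 68% | 83% | 23% |
| 2 | 144 | 96% | 54% | 73% | 10% |
| 3 | 80 | 95% | 46% | 64% | 7% |
| 4 | 80 | 94% | 36% | 55% | 3% |
| 4 | 144 | 89% | 20% | 33% | <1% |

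With HR 2, 80 events, Youden and the 50-unit grid, the 68% becomes 60% at SD 0.25 and 74% at SD 0.50. If the true relation is a smooth gradient whose Youden optimum is 1,750 (HR 1.3 to 2 per SD), another value wins in 88-93% of trials on that grid.

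**5. How far off the choice is.** With a step at the 45th percentile (55% high), HR 2 and Youden, the chosen value is more than 10 percentile points away in 23% of trials at 80 events and 12% at about 144. At HR 4 this is about 2-6%. In the setting of step 4 with 80 events, the 95% range of the selected value is about 1,530-2,230 at HR 2 and 1,690-1,940 at HR 4.

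**6. What a bootstrap interval adds.** Each of 300 trials was resampled 200 times, with Youden on the 50-unit grid. When 1,750 is true, the 95% interval contains it in 95% of trials (HR 2, 80 events), 97% (HR 2, 144) and 99% (HR 4, 80). When the true step is at 2,150 with 80 events, it still contains 1,750 in 70% (HR 2) or 14% (HR 4).

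**The case against.** The strongest reply is that the search decides nothing. The SAP calls it exploratory, and Protocol 9.4.2 places it among sensitivity analyses. The formal objectives include no threshold, and the only declared test is of continuous FcγRIIa at two-sided p < 0.05. The pilot value is already fixed at 1,750. The bleeding objective also has a continuous model, and its cut-off is chosen on ischaemic rather than bleeding events. Leave-one-out validation is planned for the prediction model. The plan names neither a Youden maximum nor a grid, so the simulated procedure is one reading of it.

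Most of this stands, and it limits the point. A reader might infer that the pilot value would be discarded in most trials whatever the method. The documents do not support that: the frequency depends on grid and effect size, and on a 250-unit grid by Youden 1,750 usually wins under a step effect. Many losses are also trivial. At HR 2 with 80 events, the Youden index at 1,750 is within 0.05 of the best in 90% of trials, and the chosen value is within 10% of 1,750 in about 81%. Nor do the documents say that a searched value will replace 1,750 throughout, or that the primary analysis is affected.

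Three things remain. The selected version is used again in SAP 5.7.2 despite the commitment to 1,750. The leave-one-out step is not stated to include the cut-off selection. The announced test of 1,750 is not described.

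**Conclusion.** The concern holds in a limited form. The plan asks whether the pilot cut-off is optimal, answers with a search in the same data without uncertainty, and reuses the answer, while also committing to 1,750. At the 2-fold design effect with a fine search, another value looks better in more than half of trials even if 1,750 is truly best. By Youden, the choice is more than 10 percentile points off in about 12-23% of trials (about 144 down to 80 events). At the pilot's roughly 4-fold effect, large misses are rare. These sizes rest on the assumed step shape, lognormal distribution, grid and criterion. The missing interval and the two competing definitions of high rest on the text alone. The exploratory status and the continuous primary analysis keep this a matter for correction in the SAP, not a threat to the main result.

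**What to change.** 1. In SAP 5.7.2, make 1,750 the main high/low definition for the binary analyses, including the bleeding model, and label any result at the data-selected cut-off exploratory. State in both documents that 11,000 on the old scale corresponds to 1,750, and whether a value exactly at the boundary is high (the protocol uses at or above, the SAP uses above).
2. In SAP 5.7.1, name the selection criterion and the grid. Repeat the whole search in bootstrap samples of subjects, for example 1,000. Report the 95% interval of the selected cut-off and the optimism-corrected performance of both the selected value and 1,750.
3. State that 1,750 will not be called non-optimal on the in-sample maximum alone. If it lies inside the interval, report that the data do not distinguish it from the selected value, not that it is confirmed as optimal.

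A stricter rule, rejecting 1,750 only when the interval for the corrected difference lies wholly above zero, is not advised. An out-of-bag version rejected 1,750 in only 3-7% of trials at HR 2 with the true step at the 75th percentile, so it would protect the pilot value by default.

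The cost is SAP wording and a few hours of programming, with no new data. The downside is that with about 80-145 events and a 2-fold effect the interval will be wide and will often not settle the question.
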